## **STUDY POPULATION**

Patients attending to the Department of Periodontology at UIC and diagnosed with PM will be recruited consecutively. One calibrated investigator ([name]) will evaluate patients for screening and will be responsible of enrolling them in the study if they fulfilled the following inclusion and exclusion criteria.

Inclusion criteria:

- (1) Presence of, at least, one titanium implant that have been more than one year in function and exhibits PM, defined as bleeding on gentle probing (0.20 N) in at least one peri-implant site.
- (2) No signs of loss of supporting bone after initial bone remodelling. In cases where baseline radiograph is available, it will be used for comparison, otherwise a maximum of 2 mm of crestal bone loss will be accepted (Sanz et al. 2012).
- (3) Presence of >1 mm of keratinized peri-implant mucosa.
- (4) Absence of systemic diseases that could influence the outcome of the therapy (i.e. controlled diabetes, with HbA1c<7, patients will be included).
- (5) Non-smoker or light smoking status in smokers (<10 cigarettes/day).

Patients will be excluded if:

- (1) Untreated periodontal conditions.
- (2) Pregnant or lactating women.
- (3) Patients who received systemic antibiotics in the last 3 months.
- (4) Patients who received treatment of PM in the past 3 months.

(5) Patients receiving corticoids or medications known to have effect on gingival growth (i.e., calcium channel antagonists, immunosuppressants or antiepileptic drugs).

In those cases diagnosed with peri-implantitis, individualized treatment will be provided, apart from the present study.

## **TREATMENT**

All patients (test and control) will be instructed to brush the implants twice daily to remove supragingival biofilms with a low-abrasive dentifrice and to use specific cylindrical or conical brushes (Interprox®, Dentaid, Barcelona, Spain) in the interproximal area. Patients will be indicated to brush under, around, and in the peri-implant crevice circumferentially. In those cases with no access for proper OHI, prosthesis will be modified according to the protocol described by de Tapia et al. 2019. The interproximal brush device used will be chosen for the patient individually, according to the interproximal space available, the thicker brush that can be used comfortably will be the selected one. It will be previously tested on the patient and its use will be taught, patients should demonstrate proficiency.

- Control group: On the affected implants, supra- and sub-gingival debridement of the implant surface, the implant neck, and the abutment will be carried out by means of a combination of ultrasonics (DTE-D5, Woodpecker®, Guilin, China) with a plastic tip (Hu-Friedy®, [name], Chicago, IL, USA) and plastic curettes (Hu-Friedy®). Finally, the prosthetic components will be polished with a rubber cup.
- Test group: No further treatment will be provided.

## **EXAMINATIONS:**

A guidebook will be prepared to standardize procedures throughout the protocol, step by step, for all questionnaires and evidence collection. The data will be transferred to a computerized database.

The study variables will be recorded in a case report form (CRF) specially designed for the study. Each study patient will be assigned a numerical code comprising a 3 digit patient code (assigned correlatively as they are included in the study). Only the study investigator will be able to identify the patient by their code.

### **Anthropometric and socio-demographic data**

An initial questionnaire will be conducted to obtain information regarding age, race, gender,

medical history, medication, and health behaviors (smoking habits). Smoking behavior will be specified as 3 categories: never smoker, former smoker, or current smoker (light smokers: < 10 cigarettes/day). Patients will be asked about their tobacco smoke exposure in terms of consumption (i.e. the number of cigarettes consumed per day); duration (i.e. the number of years of smoking); and life-time exposure (i.e. the accumulated exposure as formed by the product of consumption and duration: cigarette-years). In case of former smokers, patients will be asked about the smoke-free time following cessation.

### **Clinical, radiographic and microbiological examination**

At baseline, 1 (1m) and 3 months (3m) after treatment, two calibrated examiners ([name] and [name]) will record the following clinical variables using an electronic, pressure-calibrated probe (PA\_ON Probe, Orange Dental®, [name], Biberach, Germany), with a standardized probing force of 0.20 N.

At the full-mouth level, the following parameters will be evaluated:

- (1) Full mouth plaque Index (FMPI), assessed dichotomously at four sites per tooth (mesial, buccal, distal, and lingual).
- (2) Full mouth bleeding index (FMBI), assessed dichotomously as presence or absence of bleeding after 30 seconds of gently probing (Ainamo and Bay, 1975).
- (3) Full mouth probing pocket depth (FMPPD), measured at six sites around each tooth, except third molars.

At local level, in six sites around each implant, the following clinical variables will be recorded:

- (1) Modified plaque index (mPI) (Mombelli et al., 1987)
- (2) Modified bleeding index (mBI) (Mombelli et al., 1987), dichotomized in presence/absence of bleeding and selected as the primary outcome (BOP).
- (3) Suppuration on probing (SOP), assessed dichotomously as presence or absence of suppuration within 30 seconds after probing.
- (4) Implant probing pocket depth (PPDi), measured from the mucosal margin to the bottom of the probable pocket.
- (5) Implant mucosal recession (MRI), measured from the implant neck to the mucosal margin.

Disease resolution will be considered when a mBI <0.16 is achieved, as it was established in the last consensus performed to develop the clinical practice guidelines on the treatment of peri-implant diseases (Herrera et al. 2023).

Individual acrylic resin occlusal stents, exhibiting six vertical grooves per implant (mesiobuccal, midbuccal, distobuccal, mesiolingual, midlingual and distolingual), will be built in order to allow a reproducible direction and angulation during probing.

A periapical radiograph of all implants involved in the study will be taken using a paralleling cone technique and a film-holder (7mA- 60kV/20ms) at baseline and at 3 months after treatment, in order to detect any loss of supporting bone.

Furthermore, sampling for microbiological test will be conducted at baseline, 1m and 3months after treatment.

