## 2. Objectives

### **-Primary objective:**

Evaluate the resolution of the disease, by means of reduction of modified bleeding index (mBI), by individualized OHI and proper oral hygiene measures conducted by the patient after 1 and 3 months of protocol instauration in comparison to the combination of individualized OHI and professional mechanical debridement.

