## **SAMPLE SIZE CALCULATION**

The unit of analysis will be set at the patient. In those patients with more than one implant fulfilling the inclusion criteria, a mean of the implants included will be taken into consideration for the analysis. Sample size was calculated according to the main outcome “complete disease resolution”. Taking into account that previous studies showed a disease resolution around 66.6% (de Tapia et al. 2019) after treatment by means OHI and mechanical debridement, we estimate that at least 50% of patients receiving OHI as a single therapy could present a complete resolution. Accepting an alpha risk of 5% and a beta risk of 10% in a two-sided test, 28 subjects are necessary. It has been anticipated a drop-out rate of 15%. In order to include a second group of patients receiving an usual management as control group, we will include a total of 56 patients (28 in each group).

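### The primary outcome points to binary resolution, but the objective is worded as a reduction in mBI, no primary visit is named, and the rule for several implants gives no defined yes/no result per patient

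*Combined protocol and SAP*

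**What the plan says.** Four places in the combined protocol and SAP bear on the primary outcome.

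- **Section 2, Primary objective:** "Evaluate the resolution of the disease, by means of reduction of modified bleeding index (mBI"), assessed "after 1 and 3 months of protocol instauration". The two visits are given equal standing.
- **Section 4, Clinical, radiographic and microbiological examination:** mBI is recorded at six sites per implant, "dichotomized in presence/absence of bleeding and selected as the primary outcome (BOP"). The same section adds: "Disease resolution will be considered when a mBI <0.16 is achieved".
- **Section 4, Sample size calculation:** "Sample size was calculated according to the main outcome" of complete disease resolution, and it is assumed that "at least 50% of patients receiving OHI as a single therapy could present a complete resolution". The patient is the unit of analysis. Where a patient has more than one eligible implant, "a mean of the implants included will be taken into consideration for the analysis".
- **Section 5, Results analysis:** tests are listed by type of variable (chi-squared or Fisher's exact for qualitative, t-test or Mann-Whitney among others for quantitative, Wilcoxon or McNemar for change from baseline), with a significance level of 0.05. None is tied to the primary comparison between groups. The one model that names resolution is a logistic regression on initial mBI, which serves a secondary objective.

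Two definitions give the standard against which to read these. The Introduction equates disease resolution with absence of bleeding on probing. The inclusion criteria count an implant as having mucositis when it is "defined as bleeding on gentle probing (0.20 N) in at least one peri-implant site".

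**The concern.** A reduction in mBI is a quantity, while resolution is a yes/no result. They call for different tests and can give different answers. With two visits unranked, the visit that carries the primary conclusion could be settled after the data are seen.

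The second gap is more technical. Eligibility requires at least one affected implant, so patients with several are expected, and the plan has a rule for them. That rule averages, but the plan does not say whether the cut-off comes before or after the averaging. One order can label a patient completely resolved while an implant still meets the bleeding part of the entry definition. The other order does not yield a yes/no value at all. What is at stake is who counts as resolved, and whether the resolution rates behind the sample size describe the outcome that will be analysed.

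**Working it through.** **1. The cut-off for one implant.** Inputs: six sites per implant and a cut-off of 0.16 (examination section). Score each bleeding site 1.

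- No bleeding site: 0/6 = 0, resolved.
- One bleeding site: 1/6 = 0.167, not below 0.16, not resolved.

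So for a patient with one implant, mBI <0.16 and absence of bleeding are the same criterion. The two binary statements agree.

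**2. The cut-off applied to the patient mean.** With k implants there are 6k sites, and the mean is (sites scoring 1)/(6k). The largest number of bleeding sites that still passes is:

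| Implants k | Sites | Most bleeding sites with mean <0.16 | Mean |
|---|---|---|---|
| 1 | 6 | 0 | 0 |
| 2 | 12 | 1 | 0.083 |
| 3 | 18 | 2 | 0.111 |
| 4 | 24 | 3 | 0.125 |

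Up to k-1 bleeding sites pass. With two implants, one may still bleed at one site. With three, two may each bleed at one site. Such implants still meet the bleeding criterion for entry and fail the Introduction's description of resolution.

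**3. The cut-off applied per implant, then averaged.** One resolved implant of two gives (1 + 0)/2 = 0.5. Chi-squared, Fisher's exact test and logistic regression need a yes/no value, and no rule converts 0.5 into one.

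**4. The visit (illustration).** Inputs from the plan: 28 per group, two-sided 0.05, resolution rates of 50% and 66.6% (midpoint (50 + 66.6)/2 = 58.3%). Assumptions not in the plan: significance at either visit may count as the primary result; the true rate p is the same in both groups and at both visits; the correlation phi between visits is 0.3, 0.5 or 0.8.

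Within a patient, P(resolved at both visits) = p² + phi·p(1-p). For p = 0.583 and phi = 0.5 this is 0.340 + 0.5 × 0.243 = 0.461. The either-visit rate is 1 - P(neither visit significant), summed exactly over all outcomes in the two groups.

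| Chi-squared, true rate | One visit | Either visit, phi 0.3 / 0.5 / 0.8 |
|---|---|---|
| 50% | 4.5% | 8.6 / 8.2 / 7.0% |
| 58.3% | 4.7% | 8.9 / 8.5 / 7.3% |
| 66.6% | 5.2% | 9.9 / 9.5 / 8.1% |

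With Fisher's exact test throughout, the rates are 2.3-2.8% at one visit and 3.8-5.4% at either visit. Section 5 moves to Fisher when a frequency is below 5. The smallest expected count here is 28 × (1 - 0.666) = 9.4, so if that rule refers to expected counts, chi-squared would usually apply.

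Whether 28 per group is enough is a separate question, and nothing here depends on it.

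**The case against.** The strongest reply is that the intention is plain. The primary objective opens with resolution, the examination section selects dichotomised bleeding, the sample size section calls complete resolution the main outcome, and the Introduction ranks a mere reduction in bleeding below resolution. Section 5 then supplies chi-squared or Fisher for a binary outcome. This largely stands: a careful reader would infer binary resolution and that test. What remains is the objective's wording as a reduction, and the visit, which cannot be inferred because both are named equally.

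A second reply is that 0.16 lies just below 1/6, the value for one bleeding site on one implant, so it looks like an implant-level cut-off under which no bleeding implant passes. This is fair. A reader might infer that the plan will count still-bleeding patients as resolved. The documents do not support that, since they do not state the level, and the implant-level reading is at least as plausible. That reading still leaves the step from implants to patient undefined (step 3 of the working).

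A third reply is that no inflation of error has been shown. That is also correct. A reader might infer that the trial has a 7-10% false-positive rate. That needs an either-visit rule that the plan never states, and under Fisher's exact test the rate stays close to or below 5%.

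**Conclusion.** The point holds in limited form. The plan leans towards a binary primary outcome, but the objective's wording does not match it, the primary visit is unnamed, the primary between-group test has to be inferred, and the patient-level outcome is not fully defined for anyone with more than one included implant. It would be too strong to say that the whole primary analysis is open to choice, because the main outcome is named and a test for it can be inferred from its type.

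The wording and visit gaps affect every patient. The implant rule affects only patients with several implants. Their number is not given, so the size of that effect is unknown, and it is zero with one implant each. The arithmetic on the cut-off is exact, given that each bleeding site scores 1. The error rates only illustrate what an unranked pair of visits could allow, under the stated assumptions. The gap merits correction before analysis, because the primary result cannot at present be computed in one agreed way.

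**What to change.** - **Section 2 and the examination and sample size sections:** state one patient-level binary outcome, complete resolution, met only when every included implant has mBI <0.16 (that is, no bleeding site), at one named visit. Three months is a reasonable example, being the end of follow-up.
- **Section 5:** name the single primary between-group analysis of that outcome. Its form, a superiority test or a comparison against a margin, should be set once the superiority aim in the Introduction is reconciled with the hypotheses in section 3, which expect oral hygiene instruction alone to do as much as the combination. If a chi-squared or Fisher's exact test is used, choose between them in advance.
- **Secondary outcomes:** list 1-month resolution and change in mBI here, reported with 95% confidence intervals.

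The cost is wording, with no new data or visits. One month and change in mBI lose any claim to primary status. Requiring every implant to be free of bleeding may lower the resolution rates, so the sponsor should check that the 66.6% and 50% in the sample size section refer to this definition.

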## **5. Results analysis**

The data contained in the CRFs will be entered into a database for data analysis and preparation of the final report.

The socio-demographic and clinical characteristics and other variables of interest of the patients included in the study will be described. Data will be presented as mean  $\pm$  SD; categorical data will be shown as percentage of positive patients.

The relationship between two qualitative variables will be calculated using the chi-squared test or Fisher's exact test (frequency  $< 5$ )

For ordinal variables, linear regression will be calculated using Kendall's tau coefficient.

Quantitative variables will be compared using the Student's t-test (< 2 categories), analysis of variance [ANOVA] (> 2 categories), linear regression test and Scheffé's multiple comparisons test or U Mann Whitney.

The linear relationship between the quantitative variables will be calculated using Pearson's correlation coefficient or Spearman's rank correlation test (when variable not normally distributed).

Changes *versus* baseline will be analyzed by Wilcoxon non-parametric test or Mc Nemar test.

A logistic regression model will be set in order to determine whether the initial extent of the inflammation, mBI, is related to disease resolution

Level of significance will be set at 0.05. The SPSS version 19.00 software (SPSS Inc., Chicago, IL, USA) will be used for all analyses.

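### Averaging mBI over implants before applying the <0.16 cut-off lets a multi-implant patient count as completely resolved while an included implant still bleeds

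*Combined protocol and SAP*

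**What the plan says.** Three parts of the protocol together determine how a patient is coded.

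- **Clinical, radiographic and microbiological examination.** The section introduces the implant measurements with "At local level, in six sites around each implant, the following clinical variables will be recorded". The mBI is "dichotomized in presence/absence of bleeding and selected as the primary outcome (BOP"). The cut-off follows: "Disease resolution will be considered when a mBI <0.16 is achieved". This sentence does not say whether the mBI is that of an implant or of a patient.
- **Sample size calculation.** "The unit of analysis will be set at the patient". The next sentence reads: "In those patients with more than one implant fulfilling the inclusion criteria, a mean of the implants included will be taken into consideration". Then: "Sample size was calculated according to the main outcome", which is named as complete disease resolution.
- **Results analysis (section 5).** For categorical data: "The relationship between two qualitative variables will be calculated using the chi-squared test or Fisher's exact test". For the baseline-severity question: "A logistic regression model will be set in order to determine whether the initial extent of the inflammation, mBI, is related to disease resolution". Both need one yes/no value per patient. The section adds no rule for deriving it.

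Under Study population, inclusion criterion 1 matters too: a single bleeding site on gentle probing is enough for an implant to have PM.

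**The concern.** A cut-off of 0.16 on six sites scored 0 or 1 lies just below one bleeding site in six. At implant level it is therefore a rule of no bleeding at all, which fits an outcome called complete resolution. Once the quantity being cut is a mean over several implants, the denominator grows and the same number becomes a tolerance for residual bleeding. That tolerance increases with the number of implants.

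The meaning of the outcome that sized the trial is at stake. A reported complete-resolution rate could mix one-implant patients who have no bleeding with multi-implant patients in whom some implants still have the disease. The logistic model of resolution on initial mBI would use the same mixed outcome. With the planned 28 patients per group, each patient whose coding depends on the rule moves that group's rate by 1/28 = 3.6 percentage points.

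**Working it through.** **Inputs from the protocol.** Six sites per implant, each scored 0 or 1; cut-off strictly below 0.16; patient as unit; mean over included implants; every included implant has at least one bleeding site at entry.

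**Formula.** Every implant contributes six sites, so the mean over *k* implants with *b* bleeding sites in total is *b*/(6*k*). The patient is resolved if *b*/(6*k*) < 0.16.

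**Largest number of bleeding sites that still passes.**

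| Implants (k) | Sites (6k) | Largest b that passes | Mean | Next value |
|---|---|---|---|---|
| 1 | 6 | 0 | 0 | 1/6 = 0.167, fails |
| 2 | 12 | 1 | 0.083 | 2/12 = 0.167, fails |
| 3 | 18 | 2 | 0.111 | 3/18 = 0.167, fails |
| 4 | 24 | 3 | 0.125 | 4/24 = 0.167, fails |
| 5 | 30 | 4 | 0.133 | 5/30 = 0.167, fails |
| 6 | 36 | 5 | 0.139 | 6/36 = 0.167, fails |

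For 2 to 6 implants, *k* − 1 bleeding sites pass. If they lie on different implants, *k* − 1 of the *k* implants still bleed.

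**At baseline.** The smallest possible mean is *k*/(6*k*) = 0.167, so nobody is resolved at entry under the mean rule. From that minimum, clearing one site is enough.

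- Two implants with one bleeding site each: 2/12 = 0.167 at baseline. One site clears and the other implant does not change: 1/12 = 0.083, coded as resolved. The second implant still meets inclusion criterion 1.
- Four implants with one bleeding site each: 4/24 = 0.167 at baseline. One site clears: 3/24 = 0.125, coded as resolved, with three of four implants still bleeding.

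**The cut-off applied to each implant.** If every included implant must be below 0.16, one bleeding site on any implant gives 1/6 = 0.167 and fails. The number allowed is 0 for any *k*, so the outcome has the same meaning in every patient.

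**Sensitivity to scoring.** The counts assume the 0/1 scoring that the protocol states. If graded scores entered the mean instead, one site scored 2 on two implants would give 2/12 = 0.167 and fail, while one site scored 1 would still give 0.083 and pass. The counts in the table are then upper limits, and the problem remains.

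**The case against.** The strongest reply is that the plan does contain a rule: the patient is the unit, implants are averaged, and a cut-off on mBI is given. This is right. A reader might infer that the resolution outcome has no patient-level definition at all, but the two sections together give a codable one. The objection here is to what that rule produces. A reader might also suppose that each implant is first coded yes/no and the codes then averaged, giving 0, 0.5 or 1 with two implants. That is strained, because the cut-off is set on mBI, which can be averaged directly.

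A reader might go further and say that the rule contradicts the Introduction, which equates resolution with absence of bleeding. That text describes the aims of treatment in general and also accepts a reduction in bleeding sites. It does not bind the trial's outcome. The conflict that stands is narrower: with the word complete in the main outcome, and with the entry definition of PM.

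The guideline cited for the cut-off may state its level. Even so, the averaging is specified in this protocol and must be reconciled with the cut-off here. The guidebook promised under Examinations concerns questionnaires and data collection, with no mention of deriving outcomes.

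Finally, the same rule applies in both randomised arms and one-implant patients are unaffected. That stands, and it limits the finding. It is also fair that requiring every implant to clear is a choice: stating the mean rule openly would remove any doubt about coding. It would not make the outcome match its name.

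**Conclusion.** The point holds in a limited form and should be fixed. On the natural reading of the plan, complete disease resolution means no bleeding site in a one-implant patient, but up to 1 of 12, 2 of 18 or 3 of 24 bleeding sites with 2, 3 or 4 implants. These counts are exact under the stated 0/1 scoring and need no model.

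The finding is confined to patients with two or more included implants and limited residual bleeding. The documents do not give the share of such patients, although the averaging sentence shows that they are expected.

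Two stronger conclusions are not supported. The first is bias in the comparison of arms: nothing in the documents shows that the rule would affect one arm more than the other. The second is a definite inflation of the resolution rate. For two-implant patients, the gap between the mean rule and an every-implant rule is the share with exactly 1 of 12 sites bleeding. Suppose that 66.6% of single implants are free of bleeding and that all sites are independent. The chance that a site bleeds is then s = 1 − 0.666^(1/6) = 0.0655, and the gap is 12 × 0.0655 × 0.9345^11 = 0.37. Under a beta-binomial model with an assumed correlation of 0.7 shared across the patient's sites, it is 0.06. The correlations, and the use of 66.6% as a single-implant rate, are assumptions outside the documents. The range of 6 to 37 points only shows that the size is unknown. It is not an estimate for this trial.

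**What to change.** In the examination section and the sample size section, state that a patient is resolved only if every included implant is individually below 0.16, that is, has no bleeding at any of its six sites. Keep the mean over implants for the quantitative mBI outcome only. In section 5, name the every-implant version as the yes/no outcome for the chi-squared or Fisher comparison and for the logistic model. Report the mean-based <0.16 version as a sensitivity analysis, with the number of included implants per patient by arm. State which definition the 66.6% and 50% planning rates refer to, and recheck them if it differs.

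The cost is a few sentences, with no new measurements. The downside is that resolution rates in multi-implant patients will be equal to or lower than under the mean rule and will depend on how many implants a patient has, which is why implant counts by arm are needed. The change should be made before outcome data are seen, so that the choice of rule cannot be influenced by the results.
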